7.1.5.3.2. Sponsor Responsibility

If a serious unexpected adverse event is believed to be related to the IMP or study procedures, the sponsor will take appropriate steps to notify all investigators participating in sponsored clinical studies of TEV-53275 and the appropriate competent authorities (and IEC/IRB, as appropriate).

In addition to notifying the investigators and competent authorities (and IEC/IRB, as appropriate), other action may be required, including the following:

- altering existing research by modifying the protocol
- discontinuing or suspending the study
- modifying the existing consent form and informing all study participants of new findings
- modifying listings of expected toxicities to include adverse events newly identified as related to TEV-53275

7.1.6. Protocol-Defined Adverse Events of Special Interest for Reporting to the Global Patient Safety & Pharmacovigilance Department

For the purposes of this protocol, the following are considered PDAESI for expedited reporting to the GPSP department:

- systemic severe reactions (including anaphylaxis) that follow the diagnostic criteria for anaphylaxis as outlined by the 2006 Joint National Institute of Allergy and Infectious Disease/Food Allergy and Anaphylaxis Network (NIAID/FAAN) Second Symposium on Anaphylaxis ([Sampson et al 2006, \[Appendix H\]](#)).
- opportunistic infections as listed in the Panel on Opportunistic Infections in HIV-Infected Adults and Adolescents guidelines for the prevention and treatment of opportunistic infections in HIV-infected adults and adolescents: recommendations from the Centers for Disease Control and Prevention, the National Institutes of Health, and the HIV Medicine Association of the Infectious Diseases Society of America ([Appendix I](#)).
- helminth infections
- malignancies (including non-melanoma skin cancer)

The process for reporting these PDAESI is the same as that for reporting a serious adverse event (see Section [7.1.5.3](#)). These events can be either serious or nonserious, according to the criteria outlined in Section [7.1.5.1](#).

7.1.7. Protocol-Defined Adverse Events of Special Interest that do not Require Reporting to the Global Patient Safety & Pharmacovigilance Department

Injection site findings will be assessed using a standardized scale as described in Section [7.8](#). Injection site findings will not be captured as adverse events unless they fulfill characteristics that are beyond those in the specified forms/scales (eg, necrosis, abscess, etc.) or fulfill seriousness criteria; if fulfilled, they must be recorded and reported as specified in Section [7.1.2](#).

7.1.8. Protocol Deviations Because of an Adverse Event

If a patient experiences an adverse event or medical emergency, deviations from the protocol may be allowed on a case-by-case basis. To ensure patient safety, after the event has stabilized or treatment has been administered (or both), the investigator or other physician in attendance must contact the CRO medical monitor as soon as possible to discuss the situation. The investigator, in consultation with the sponsor, will decide whether the patient should continue to participate in the study.

7.2. Pregnancy

Any female patient becoming pregnant during the study will be discontinued from the study.

All pregnancies of women participating in the study that occur during the study, or within 5 half-lives after IMP administration, or is reported to the investigator, are to be reported immediately to the CRO medical monitor, and the investigator must provide the sponsor (LSO) with the completed pregnancy form. The process for reporting a pregnancy is the same as that for reporting a serious adverse event (Section [7.1.5.3.1](#)) but using the pregnancy form.

The investigator is not required to report patients who are found to be pregnant between screening and baseline, provided no protocol-related procedures were applied.

All female patients who become pregnant will be monitored for the outcome of the pregnancy (including spontaneous, elective, or voluntary abortion). If the pregnancy continues to term, the outcome (health of the infant up to 8 weeks of age), including details of birth and presence or absence of any birth defect, congenital abnormalities, or maternal and newborn complications, will be reported to the sponsor. Any complication of pregnancy during the study and any complication of pregnancy that the investigator becomes aware of after withdrawal from the study will be reported as an adverse event or serious adverse event, as appropriate.

Since there is no evidence of reproductive risk, human mutagenicity or genotoxicity for this IMP, female partners will not be asked to sign an ICF to monitor the outcome of the pregnancy.

If the pregnancy in the woman participating in the study does not continue to term, 1 of the following actions will be taken:

- for a spontaneous abortion, report as a serious adverse event.
- for an elective abortion due to developmental anomalies, report as a serious adverse event.
- for an elective abortion not due to developmental anomalies, report on the pregnancy form; do not report as an adverse event.

7.3. Medication Error and Special Situations Related to the Investigational Medicinal Products

Any administration of IMP that is not in accordance with the study protocol should be reported as a protocol deviation and in the patients' source documents, regardless of whether or not an adverse event occurs as a result. When meeting important protocol deviation criteria, all instances of incorrect IMP administration should be categorized as "Noncompliance to Investigational Medicinal Product (IMP)."

The following are types of medication errors and special situations:

- **medication error:** Any unintentional error in the prescribing, dispensing, or administration of a medicinal product while in the control of the healthcare professional, patient, or consumer.
- **overdose:** Administration of a quantity of a medicinal product given per administration or cumulatively which is above the maximum recommended dose according to the protocol or authorized product information as applicable. Clinical judgment should always be applied. Any dose of IMP (whether the test IMP or placebo IMP), whether taken intentionally or unintentionally, in excess of that prescribed must be immediately reported to the sponsor.
- **misuse:** Any intentional therapeutic use of a drug product in an inappropriate way or opioid use contrary to the directed or prescribed pattern of use, regardless of the presence or absence of harm or adverse effects. Examples: under usage, erratic or disorganized use, inappropriate use (for anxiety), use in conjunction with alcohol or illegal substances, overuse.

- **abuse:** Any intentional, nontherapeutic use of a drug product or substance, even once, for the purpose of achieving a desirable psychological or physiological effect, or intentional use of an opioid for a nonmedical purpose, such as euphoria or altering one's state of consciousness.
- **off-label use:** Situations where an IMP is intentionally used for a medical purpose not in accordance with the protocol or authorized product information as applicable.
- **occupational exposure:** Exposure to an IMP, as a result of one's professional or non-professional occupation.
- **breastfeeding:** Suspected adverse events which occur in infants following exposure to a medicinal product from breast milk.

7.4. Clinical Laboratory Tests

All clinical laboratory test results outside the reference range will be judged by the investigator as belonging to one of the following categories:

- abnormal and not clinically significant
- abnormal and clinically significant

A laboratory test result that is judged by the investigator as clinically significant will be recorded both on the source documentation and the CRF as an adverse event, and monitored as described in Section 7.1.2. A laboratory or diagnostic test abnormality (once confirmed by repeated testing) that results in the withdrawal of the patient from the study, the temporary or permanent withdrawal of IMP or medical treatment, or further diagnostic work-up may be considered adverse events. If further diagnostic work-up of an abnormal laboratory result leads to the investigator concluding that the initial abnormality was not clinically significant, it is at the investigator's discretion whether or not the result triggering the work-up is an adverse event. (Note: Abnormal laboratory or diagnostic test results at the screening visit that preclude a patient from entering the study or receiving IMP are not considered adverse events.)

Details of clinical laboratory tests will be included in the study reference manual.

For details of the management of study activities during COVID-19 outbreaks, see [Appendix N](#).

7.4.1. Serum Chemistry, Hematology, and Urinalysis

Clinical laboratory tests (serum chemistry, hematology, and urinalysis) will be performed at the time points detailed in [Table 2](#). Clinical laboratory tests will be performed using the central laboratory. Details are provided in [Appendix A](#). Specific serum chemistry, hematology and coagulation laboratory tests to be performed are listed in [Table 5](#).

Table 5: Clinical Laboratory Tests

Serum Chemistry	Hematology and Coagulation
Calcium (Ca)	Hematocrit (Hct)
Phosphorous	Hemoglobin (Hb)
Sodium (Na)	Red blood cell (RBC) count
Potassium (K)	White blood cell (WBC) count
Chloride (Cl)	Platelet count
Creatinine	Mean corpuscular hemoglobin (MCH)
Creatinine phosphokinase (CPK)	Mean corpuscular hemoglobin concentration (MCHC)
Glucose	Mean corpuscular volume (MCV)
Blood urea nitrogen (BUN)	Mean Platelet Volume (MPV)
Alanine aminotransferase (ALT/SGPT)	Red Cell Distribution Width (RDW)
Aspartate aminotransferase (AST/SGOT)	CBC, Nucleated RBC (%), abs)
Gamma-glutamyl transpeptidase (GGT)	WBC Differential
Alkaline phosphatase (ALP)	
 - Basophils (%), abs) - Eosinophils (%), abs) - Immature granulocyte (%), abs) - Lymphocytes (%), abs) - Monocytes (%), abs) - Neutrophils, Total (%), abs)
Bicarbonate	
Protein, total	
Albumin	
Bilirubin, total	

7.4.2. Other Clinical Laboratory Tests

7.4.2.1. Serology Tests

At screening, patients will be tested for HBsAg, antibodies to HCV, and HIV Types 1 and 2. Patients with confirmed positive results will not be eligible to participate in the study.

7.4.2.2. Follicle Stimulating Hormone

At screening, women who have been amenorrheic for at least 1 year without an alternative medical cause will have a serum FSH assessment to confirm postmenopausal status (an increased concentration of FSH of more than 35 IU/L in women not using hormonal contraception or hormonal replacement therapy).

7.4.2.3. Human Chorionic Gonadotropin Tests

β -HCG tests in urine will be performed for women of childbearing potential as detailed in [Table 2](#).

7.4.2.4. COVID-19 Testing

Testing of patients asymptomatic for COVID-19 active infection may be conducted at the discretion of the investigator within 72 hours of any visit where spirometry assessments are to be conducted or as required by health authorities, local ethics committees, or study center SOPs. The testing may be conducted by the central laboratory or locally depending on feasibility. The

testing may be conducted by the central laboratory or locally depending on feasibility. Positive tests that measure COVID-19 antigen must be confirmed by RT-PCR.

For details of the management of study activities during COVID-19 outbreaks, see [Appendix N](#).

7.5. Physical Examinations

Physical examinations will be performed at the time points detailed in [Table 2](#). Height in centimeters and weight in kilograms will be recorded at screening. Weight only will be measured at other times specified. Body mass index will be determined.

A full physical examination will include, at a minimum, head, eyes, ears, nose, and throat (HEENT), chest, cardiovascular, abdominal, skin examination and abbreviated neurological examination including cranial nerves, deep tendon reflexes and strength. A brief physical examination will include, at a minimum, chest, cardiovascular, abdominal, and skin examinations.

Any physical examination finding that is judged by the investigator as clinically significant (except at the initial screening visit, which will be captured as medical history) may be considered an adverse event, recorded on the CRF and the source document, and monitored as described in [Section 7.1.2](#).

For details of the management of study activities during COVID-19 outbreaks, see [Appendix N](#).

7.6. Vital Signs

Vital signs (pulse rate, blood pressure [systolic/diastolic], respiratory rate, and body temperature) will be measured at the time points detailed in [Table 2](#). All vital signs results outside the reference ranges will be judged by the investigator as belonging to one of the following categories:

- abnormal and not clinically significant
- abnormal and clinically significant

Before blood pressure and pulse are measured, the patient must rest in a supine, semi-recumbent or seated position for at least 5 minutes. The same position and arm should be used as much as possible each time vital signs are measured for a given patient. If the opposite arm is used it will not be collected as a protocol deviation. For any abnormal vital signs value, the measurement should be repeated as soon as possible. Any vital signs value that is judged by the investigator as clinically significant will be recorded both on the source documentation and the CRF as an adverse event, and monitored as described in [Section 7.1.2](#).

For details of the management of study activities during COVID-19 outbreaks, see [Appendix N](#).

7.7. Electrocardiography

A 12-lead ECG will be recorded at the time points detailed in [Table 2](#). Where triplicate measurements are required (DoR), each ECG will be taken within 1 to 5 minutes of the previous one.

Standard ECGs parameters will be recorded using a centralized process and the ECG will be interpreted locally by the principal investigator (or qualified physician). Additionally, a qualified

central reader will interpret all ECG. In cases of disagreement, the interpretation by the central reader should be used. All ECG results outside the reference ranges will be judged by the investigator (or qualified physician) as belonging to one of the following categories:

- abnormal and not clinically significant
- abnormal and clinically significant

Any ECG finding that is judged by the investigator (or qualified physician) as clinically significant (except at the screening visit) will be considered an adverse event, recorded on the source documentation and in the CRF, and monitored as described in Section 7.1.2.

For details of the management of study activities during COVID-19 outbreaks, see [Appendix N](#).

7.8. Assessment of Local Tolerability and Pain

Local tolerability at the injection site (erythema, ecchymosis, induration, tenderness, warmth, swelling, and pain) will be assessed using standardized scales. Patient reported pain at the injection site will be reported using a standardized 11-point pain intensity numerical response scale (NRS-11) where 0 is “No pain” and 10 is “Worst possible pain”; patients will be asked to respond to the following question: “How much pain do you feel at the drug injection site, where 0 is ‘No pain’ and 10 is ‘Worst possible pain’?”.

The assessments will be performed at approximately 1 hour after dosing ([Table 2](#)).

Severity of local tolerability symptoms should be assessed as described in [Table 6](#). Erythema, ecchymosis, and induration will be considered only if they reach a diameter of at least 5 mm. The surface diameter in millimeters will be recorded and erythema, induration, and ecchymosis at the injection site will be graded according to the diameter measurements: Absent, 5 to \leq 50 mm (mild), $>$ 50 to \leq 100 mm (moderate), and $>$ 100 mm (severe). Induration must be assessed by careful superficial palpation avoiding pressuring or squeezing the injection site.

In cases where symptoms do not resolve, assessments will proceed at each ambulatory visit. Appropriate treatment may be provided if necessary, in which case it must be recorded as concomitant medication. In case the site(s) of injection need visual representation, in addition to comments in the source documents, the injection site(s) may be photographed along with a metric ruler and patient identification number for later review. Any features that could be used to identify the patient will not be captured on the photograph.

Table 6: Severity Assessment of Local Tolerability

Test	Response
Erythema	
- Absent- Erythema surface diameter 5 to \leq50 mm (mild)- Erythema surface diameter >50 to \leq100 mm (moderate)- Erythema surface diameter >100 mm (severe)
Ecchymosis	
- Absent- Ecchymosis surface diameter 5 to \leq50 mm (mild)- Ecchymosis surface diameter >50 to \leq100 mm (moderate)- Ecchymosis surface diameter >100 mm (severe)
Induration	
- Absent- Induration surface diameter 5 to \leq50 mm (mild)- Induration surface diameter >50 to \leq100 mm (moderate)- Indurations surface diameter >100 mm (severe)
Tenderness	
- None
Warmth	
- Mild
Swelling	
- Moderate- Severe

Injection site findings will not be captured as adverse events unless they fulfill characteristics that are beyond those in the specified forms/scales (eg, necrosis, abscess, etc.) or fulfill seriousness criteria; if fulfilled, they must be recorded and reported as specified in Section 7.1.2.

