^{dd} Patients should be trained on the proper use of the handheld device to measure lung function including performing readings prior to taking daily asthma maintenance medication and prior to taking rescue medication within 6 hours of testing (as possible). The patient should be retrained at each visit as indicated.

^{ee} Review compliance with handheld device measurements and with diary entries, including the proper use in relation to asthma maintenance medication and rescue medication use/timing.

^{ff} Patients who meet the requirements for randomization, after the procedures for specimen collection and other testing, will each receive 4 sc injections in the abdomen, administered by a qualified health care provider (according to local regulations) who is prepared to manage anaphylaxis, as described in the study reference manual. The kit number and location will be recorded in the source documents and entered in the CRF for each of the 4 injection site locations along with any injection site reactions evaluated at approximately 1 hour after dosing. If the patient develops clinical symptoms, vital signs should be recorded and the patient should be assessed for anaphylaxis/hypersensitivity reactions. Before leaving the clinic, patients will additionally be advised of symptoms/signs for which they should seek medical advice or medical treatment.

^{gg} Evaluation of injection site for reaction will be performed at approximately 1 hour after dosing using the injection site CRF. Injection site findings will not be captured as adverse events unless they fulfill characteristics that are beyond those in the specified forms/scales (eg, necrosis, abscess, etc.) or fulfill seriousness criteria; if fulfilled, they must be recorded and reported.

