- inquire about adverse events
- inquire about concomitant medications
- COVID-19 symptoms inquiry

4. Procedures During Double-Blind Treatment Period (Visits 4 through 7)

a. Visit 4 (Week 1 [Days 3±2])

The following procedures will be performed:

- pulmonary function testing (spirometry)
- hematology (blinded CBC with differential analysis)
- obtain a blood sample for pharmacokinetics (serum IMP concentration)
- obtain a blood sample for serum biomarker (IL-5) analysis
- dispense/collect rescue medication (if needed)
- assess CAEs
- inquire about adverse events
- inquire about concomitant medications
- COVID-19 symptoms inquiry

b. Visit 5 (Week 2 [Day 14±2])

The following procedures and assessments will be performed:

- brief physical examination (to include, at a minimum, chest, cardiovascular, abdominal, and skin examinations)
- pulmonary function testing (spirometry)
- hematology (blinded CBC with differential analysis)
- obtain a blood sample for pharmacokinetics (serum IMP concentration)
- obtain a blood sample for serum biomarker (IL-5) analysis
- vital signs measurements
- complete ACQ-6
- review compliance with diary and study requirements
- dispense/collect rescue medication (if needed)
- assess CAEs
- inquire about adverse events
- inquire about concomitant medications
- COVID-19 symptoms inquiry

c. Visit 6 (Week 4 [Day 28±2])

The following procedures and assessments will be performed:

- brief physical examination (to include, at a minimum, chest, cardiovascular, abdominal, and skin examinations)
- pulmonary function testing (spirometry)
- hematology (blinded CBC with differential analysis)
- serum chemistry tests
- obtain a blood sample for pharmacokinetics (serum IMP concentration)
- obtain a blood sample for biomarker (IL-5) analysis
- urine pregnancy test for women of childbearing potential (β HCG)
- vital signs measurements
- complete ACQ-6
- complete ACT
- review compliance with diary and study requirements
- dispense/collect rescue medication (if needed)
- assess CAEs
- inquire about adverse events
- inquire about concomitant medications

- COVID-19 symptoms inquiry

d. Visit 7 (Week 8 [Day 56±2]):

The following procedures and assessments will be performed:

- brief physical examination (to include, at a minimum, chest, cardiovascular, abdominal, and skin examinations)
- pulmonary function testing (spirometry)
- hematology (blinded CBC with differential analysis)
- serum chemistry tests

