8.4. Injection Site Assessments

Local tolerability at the injection site (erythema, ecchymosis, induration, tenderness, warmth, swelling, and pain) will be assessed using standardized scales. Patient reported pain at the injection site will be reported using a standardized 11-point pain intensity numerical response scale (NRS-11) where 0 is “No pain” and 10 is “Worst possible pain”; patients will be asked to

respond to the following question: "How much pain do you feel at the drug injection site, where 0 is 'No pain' and 10 is 'Worst possible pain'?".

Table 2: Severity Assessment of Local Tolerability

Test	Response
Erythema	
 - Absent - Erythema surface diameter 5 to \leq50 mm (mild) - Erythema surface diameter >50 to \leq100 mm (moderate) - Erythema surface diameter >100 mm (severe)
Ecchymosis	
 - Absent - Ecchymosis surface diameter 5 to \leq50 mm (mild) - Ecchymosis surface diameter >50 to \leq100 mm (moderate) - Ecchymosis surface diameter >100 mm (severe)
Induration	
 - Absent - Induration surface diameter 5 to \leq50 mm (mild) - Induration surface diameter >50 to \leq100 mm (moderate) - Indurations surface diameter >100 mm (severe)
Tenderness	
 - None
Warmth	
 - Mild
Swelling	
 - Moderate - Severe

The injection site assessments (erythema, ecchymosis, induration, tenderness, warmth, and swelling) at each visit will be summarized using descriptive statistics. For NRS-11 scale, the worst pain score overall and the pain score at each visit will be summarized descriptively.

In order to account for both placebo and TEV-53275 injections in the 600 mg dose, the summaries will be split into three columns: placebo injections, TEV-53275 injections and total.

The data will be listed using safety analysis set, sorted by treatment group, subject ID, visit, and injection. The study medication administered for each injection will also be listed.

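### A non-serious, in-scale injection-site reaction that first appears after the 1-hour check has no required route into the injection-site data or the adverse-event data

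*Protocol*

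**What the plan says.** Each patient receives four 3 mL injections on one occasion at V3 (Protocol 5).

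- **When sites are scored.** Protocol 7.8: "The assessments will be performed at approximately 1 hour after dosing". Table 2 footnote gg agrees: "Evaluation of injection site for reaction will be performed at approximately 1 hour after dosing using the injection site CRF". Appendix B lists an injection-site evaluation at V3 and at no later visit.
- **When scoring is repeated.** Protocol 7.8: "In cases where symptoms do not resolve, assessments will proceed at each ambulatory visit".
- **What stays out of the adverse-event record.** Protocol 7.1.7, with the same rule in 7.8 and footnote gg: "Injection site findings will not be captured as adverse events unless they fulfill characteristics that are beyond those in the specified forms/scales". The other exception is for findings that are serious: "or fulfill seriousness criteria; if fulfilled, they must be recorded and reported as specified in Section 7.1.2".
- **What is recorded if a reaction is treated.** Protocol 7.8: "Appropriate treatment may be provided if necessary, in which case it must be recorded as concomitant medication".
- **What is analysed.** SAP 8.4 summarises the scale items by visit and, for NRS-11, "the worst pain score overall and the pain score at each visit will be summarized descriptively". Its columns separate placebo injections from TEV-53275 injections.

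Local tolerability is a secondary safety endpoint (Protocol 2.1), and Protocol 3.3 names injection-site findings among the adverse events of special interest.

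**The concern.** It is reasonable to exempt in-scale findings from adverse-event reporting when a dedicated form collects them instead. That holds for reactions present at 1 hour. For a reaction that starts later, the exemption still applies but nothing requires the dedicated form to be completed. The tables would then describe reactions visible at 1 hour and their follow-up, while a reader would take them as the local tolerability of the product over the study. The matter bears on a stated endpoint and a named event of special interest. It does not touch the primary efficacy analysis or the handling of serious events.

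**Working it through.** The plan gives no figure to reproduce. The check traces one case through the rules and then shows what an unknown late-onset share would do.

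**Step 1: one case.** Suppose all four sites are clear at 1 hour, and 60 mm erythema appears the next day and is mentioned at V4 (Day 3±2).

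1. *Injection-site CRF.* The scheduled evaluation has passed. The repeat rule covers symptoms that fail to resolve, so it presupposes a symptom already under assessment. Nothing triggers scoring of a new one.
2. *Adverse-event form.* Table 6 grades 60 mm as moderate (>50 to ≤100 mm), so the finding is within the scale. If it is not serious, it is exempt.
3. *Width of the exemption.* The top band of Table 6 is open-ended above 100 mm, and NRS-11 runs to 10. Diameter or pain alone can never take a finding beyond the scales.

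**Step 2: other places the reaction might surface.**

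| Route | Required for this case? | Feeds the SAP 8.4 tables? |
|---|---|---|
| Adverse-event questioning at each contact (7.1.2) | Yes, but an in-scale finding is then exempt | No |
| Concomitant medication (7.8) | Only if treated; holds the treatment, not the grade | No |
| Skin examination (7.5), first after dosing at V5 (Day 14±2) | A clinically significant finding may be considered an adverse event; this sits awkwardly with the 7.8 exemption | No |
| Unscheduled visit (Appendix B) | At the investigator's discretion | Not assured |
| Home visit during a COVID-19 outbreak (Appendix N) | Contingency only | Not assured |

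The adverse-event summaries in SAP 8.3 cannot recover a finding that was never entered as an adverse event. For a patient who is clear at 1 hour, the SAP 8.4 worst score is the 1-hour score unless a site chooses to record more.

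**Step 3: what an unknown share would do.** Let R be the proportion of patients whose local reaction is recorded, and L the proportion whose only reaction is late, non-serious, in-scale and not captured otherwise. True incidence is R + L. With f = L / (R + L), recorded incidence is R = (1 − f) × (R + L).

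| Assumed f | Recorded as a fraction of true |
|---|---|
| 0 | 1.00 |
| 10% | 1 − 0.10 = 0.90 |
| 25% | 1 − 0.25 = 0.75 |
| 50% | 1 − 0.50 = 0.50 |

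For the difference in percentages between an active arm (A) and placebo (P), true minus recorded is

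(R_A + L_A − R_P − L_P) − (R_A − R_P) = L_A − L_P.

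This is zero when late-only reactions are equally frequent in the two arms. The documents support no particular f and no particular L_A − L_P.

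**The case against.** The strongest opposing case has four parts.

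- **Scoring is not confined to 1 hour, and the adverse-event exemption is not absolute.** Unresolved reactions are followed at later visits. That also explains why SAP 8.4 speaks of visits and a worst score, so the SAP is not incoherent. Findings that are serious or beyond the scales must be reported. All of this stands. A reader might infer that a late reaction is recorded nowhere, or that capture is zero. The documents do not support that: treatment, source notes, a skin examination or an unscheduled visit may leave a trace. What they lack is a required route into the endpoint.
- **The evidence on the schedule is incomplete.** The injection-site row of Table 2 is not in the text available here. Appendix B is not a full list: it omits the V4 vital signs that Table 2 marks. Its silence at V4 is therefore weak evidence by itself. The timing in 7.8 and footnote gg does not depend on it.
- **The product data point to early reactions.** Protocol 1.3.1 reports that Phase 1 findings were mild except for one moderate case, which resolved over 4 hours, and that the commonest was mild erythema at 20 minutes. This makes a 1-hour check a reasoned choice. The text does not say when sites were inspected later, so it does not exclude late onset.
- **The same rules apply in every arm.** This also stands. A reader might infer a bias toward no harm, but that needs late reactions to be more frequent on active drug, and no document says so.

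**Conclusion.** The gap is real and narrow. As written, a non-serious, in-scale reaction that first appears after the 1-hour check has no required route into the injection-site data or the adverse-event data. The local-tolerability endpoint would miss such reactions if they occur.

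The size cannot be stated. The fractions above illustrate assumed values of f, and f = 0 is compatible with everything in the documents. A reader might multiply the number of treated patients by a guessed rate to count missed reactions; with no late-onset rate given, such a count has no basis. Understatement is conditional on late reactions occurring, and a distorted difference between arms is conditional on their rate differing by arm.

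Confidence is moderate, because the conclusion rests on 7.8 and footnote gg without sight of the Table 2 row. If that row marks an evaluation at V4, the gap shrinks to the wording of the exemption and of the repeat rule. The point merits correction because the change is small and concerns a named safety endpoint.

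**What to change.** 1. In Protocol 7.1.7, 7.8 and footnote gg, limit the adverse-event exemption to findings recorded on the injection-site CRF. Any finding first seen or reported after the 1-hour evaluation is then entered either on that CRF, with onset and resolution dates, or as an adverse event.
2. Use the existing injection-site page at V4 to ask about new findings since dosing, and align Table 2 and Appendix B.
3. In SAP 8.4, define the worst score over all recorded evaluations.

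The cost is protocol and SAP wording, plus one existing CRF page repeated at a visit that already takes place. Reported injection-site rates may look slightly less favourable. No dose, treatment or clinical rule changes.
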